4.3 Exclusion Criteria

- 1. Anticancer treatment during the last 30 days prior to start of treatment, including systemic therapy, radiotherapy or major surgery
- 2. Participation in a clinical trial within the last 30 days prior to study treatment
- 3. History of allogeneic tissue/solid organ transplant
- 4. Has a history of (non-infectious) pneumonitis that required steroids or current pneumonitis.
- 5. Evidence of interstitial lung disease.
- 6. cT4 tumor
- 7. Symptomatic acute cardiovascular or cerebrovascular disease
- 8. Known active HBV, HCV or HIV infection
- 9. Has any other active infection requiring systemic therapy.
- 10. Patients with active tuberculosis

- 11. Prior therapy with an anti-Programmed cell death protein 1 (anti-PD-1), anti-PD-L1, anti-Programmed cell death-ligand 2 (anti-PD-L2), anti-CD137 (4-1BB ligand, a member of the Tumor Necrosis Factor Receptor [TNFR] family), or anti-Cytotoxic T-lymphocyte-associated antigen-4 (anti-CTLA-4) antibody (including ipilimumab or any other antibody or drug specifically targeting T-cell co-stimulation or checkpoint pathways)
- 12.A diagnosis of immunodeficiency or patient is receiving chronic systemic steroid therapy or any other form of immunosuppressive therapy within 7 days prior to the first dose of trial treatment.
- 13.Patient has had a prior monoclonal antibody within 4 weeks prior to study Day 1
- 14. Patient has had prior chemotherapy, targeted small molecule therapy, or radiation therapy in history.
- 15. Has an active autoimmune disease requiring systemic treatment within the past 3 months or a documented history of clinically severe autoimmune disease, syndrome that requires systemic steroids or а or immunosuppressive agents. Subjects with vitiligo or resolved childhood asthma/atopy would be an exception to this rule. Subjects that require intermittent use of bronchodilators or local steroid injections would not be excluded from the study. Subjects with hypothyroidism stable on hormone replacement or Sjorgen's syndrome will not be excluded from the study.
- 16. Has received a live vaccine within 30 days prior to the first dose of trial treatment. [Seasonal influenza vaccines for injection are generally inactivated flu vaccines and are allowed; however, intranasal influenza vaccines (e.g., Flu-Mist®) are live attenuated vaccines, and are not allowed.]
- 17. Has known hypersensitivity to pembrolizumab or any of the constituents of the product.
- 18. Other active malignancy requiring treatment

Exceptions include basal cell carcinoma of the skin or squamous cell carcinoma of the skin that has undergone potentially curative therapy or in situ cervical cancer.

19. Lactating or pregnant women, women of child-bearing potential who do not agree to the usage of highly effective contraception methods (allowed

methods of contraception, meaning methods with a rate of failure of less than 1% per year are implants, injectable contraceptives, combined oral contraceptives, intrauterine pessars (only hormonal devices), sexual abstinence or vasectomy of the partner). Women of childbearing potential must have a negative pregnancy test (serum β -hCG) at Screening.

- 20. Any psychiatric illness that would affect the patient's ability to understand the demands of the clinical trial
- 21. Patient has already been recruited in this trial
- 22. Patient who has been incarcerated or involuntarily institutionalized by court order or by the authorities § 40 Abs. 1 S. 3 Nr. 4 AMG.
- 23. Patients who are unable to consent because they do not understand the nature, significance and implications of the clinical trial and therefore cannot form a rational intention in the light of the facts [§ 40 Abs. 1 S. 3 Nr. 3a AMG].

5 Schedule of Assessment and Procedures

Please refer to the Schedule of Assessments for an overview.

Data will be collected via an electronic Case Report Form (eCRF) for each eligible patient. The investigator should confirm eligibility of the patient according to the inclusion and exclusion criteria of the study. All patients will provide written Informed Consent before any study specific assessment is performed. A study specific assessment is defined as a procedure that is not part of the routine assessments performed for diagnostic purposes or standard care. Screening assessments should occur within 28 days of the first administration of study drug.

Patients not meeting the inclusion/exclusion criteria will not be enrolled into the study. Patients should receive their first dose of study treatment as soon as possible after they have been intended to be treated with study medication.

5.1 Study Assessments

5.1.1 Tumor assessments

All tumor evaluation is performed according to RECIST (Response Evaluation Criteria In Solid Tumors, V. 1.1, 2009, see Appendix 2 – RECIST 1.1 and table below) using CT scan or MRI scan. The baseline tumor assessment must be recorded and measured within 28 days prior to treatment start. The imaging technique for baseline tumor measurement(s) may be either computed tomography (CT, including spiral CT) or MRI according to investigator's choice and local routine standard of care. However, the same imaging technique must be used for all consecutive tumor assessments of the same patient. Whenever possible the same personnel should perform the tumor image evaluation.

All lesions identified at screening have to be assessed at each scheduled tumor measurement. Patients with measurable lesions will be eligible for inclusion. Measurable lesions must have at least one diameter of 20 mm with conventional techniques and at least 10 mm with spiral CT scan. Where there are several lesions, assessment is based on the sum of the longest diameters of the individual target lesions. Lymph nodes with a short axis of \geq 15 mm are considered measurable and assessable as target lesions. The short axis measurement should be included in the

sum of lesions in calculation of tumor response. Nodes that shrink to < 10 mm short axis are considered normal. All other pathological nodes (those with short axis \ge 10 mm but < 15 mm) should be considered non-target lesions.

In cases where there is suspicion of progression before the next scheduled assessment, an unscheduled tumor assessment should be performed.

Response Criteria

Definitions of the criteria used to determine objective tumor response/ Evaluation of target lesions:

Complete response	Disappearance of all target lesions. Any pathological lymph nodes (whether target or non-target) must have reduction in short axis to < 10 mm.
Partial response	At least a 30% decrease in the sum of diameters of target lesions, taking as reference the baseline sum diameters.
Stable disease	Neither sufficient shrinkage to qualify for PR nor sufficient increase to qualify for PD, taking as reference the smallest sum diameters on study (this includes the baseline sum if that is the smallest on study).
Progressive disease	At least a 20% increase in the sum of diameters of target lesions, taking as reference the smallest sum on study (this includes the baseline sum if that is the smallest on study). In addition to the relative increase of 20%, the sum must also demonstrate an absolute increase of at least 5 mm. In the absence to clinical deterioration, a validation scan shall be performed after 4 weeks. Treatment continuation is warranted if tumor growth ≤20% of SLD. If PD is confirmed, the date of the pervious scan is counted as time point for PD. or Appearance of one or more new lesion. Note that the appearance of a single new lesion also requires validation of progression by another scan after 4 weeks.

5.1.2 Other Clinical Assessments

5.1.2.1 ECOG Performance Status

To be eligible for study entry, patients must have an ECOG performance score of 0 to 1. The patients' ECOG performance status will be assessed at the screening visit, during treatment every 3 weeks, before surgery, and at the EOT-visit.

5.1.2.2 Medical history

Medical history including cancer and treatment history will be reviewed and recorded at screening visit (\leq 1 year before enrolment).

5.1.2.3 ECG

A 12-lead ECG will be performed at screening, pre-surgery and at EOT and during the treatment phase if clinically indicated.

5.1.2.4 Chest X-ray

Routine chest X-ray according to local standard will be performed at screening, during neoadjuvant treatment Q3W, pre- and post-surgery and at EoT.

5.1.2.5 Quality of life

Quality of life will be assessed by the EORTC QLQ-C30 questionnaire. QoL will be assessed at screening, before surgery and at EoT.

5.1.2.6 Lung function/blood gas analysis

Lung function test in order to evaluate the operability of a patient should be done prior to or at screening. Availability of an adequate lung function test is an inclusion criterion and the test should not be older than 4 weeks at screening. The tests include body plethysmography, assessment of diffusion capacity and blood gas analysis. Lung function tests should be repeated during pembrolizumab treatment Q3W, prior to surgery and at EoT.

Parameters to be assessed are: FEV1, VC, FEV/VC, TLCO, PaO₂, PaCO₂, SaO₂, pH.

5.1.2.7 Physical examination

A full physical examination will be performed at the screening visit and at EOT. During treatment a focused clinical examination at every cycle as well as pre-surgery and at discharge is sufficient.

5.1.2.8 Vital signs

Vital signs (blood pressure, heart rate, body temperature) as well as body weight will be measured at the screening visit, at each visit during treatment phase, before surgery, at dis-charge and at the EoT-visit. Body height will be measured at screening only.

5.1.2.9 Translational Research

Additional blood and tumor samples will be collected in patients as described in the translational research plan which is deposited in the ISF.

5.1.3 Safety Assessments

See section 7

5.1.4 Laboratory Assessments

Blood samples will be taken for hematological and serum chemistry monitoring at screening and every 3 weeks +/- 3 days during treatment phase, before surgery and at EOT. The local laboratory will perform the analyses and provide reference ranges.

5.2 Study Procedures

5.2.1 Screening Procedures (day -28 to 0)

NOTE: Any routine procedure which is performed during the screening window may be used as a screening assessment in this trial. Documentation of any screening procedure in the eCRF can only be performed after informed consent of the patient. All patients will be screened and screening procedures performed within 28 days prior to start of study treatment include the following:

Signed Informed ConsentObtained prior to any study specific assessment

AIO-Studien-gGmbH

Demographics and medical	○ Age, gender, race
history	 Tumor diagnosis
	 Previous and concurrent relevant diseases
	 Previous treatments
	 Tobacco consumption in pack years
Tumor measurement	See section 5.1.1
according to RECIST 1.1	
(CT or MRI)	
Tumor assessments	Whole body PET-CT and MRI brain scans (or CT
CT or MRI	brain if MRI is not feasible) are required.
Cardiac evaluation	12-lead ECG
Physical examination and	 Physical examination
vital signs	 Body height, weight
	 Vital signs measurements will include body
	temperature, pulse and blood pressure
ECOG performance status	See Appendix 1 – ECOG Performance Status
Serum pregnancy test	A serum pregnancy test will be performed in pre-
	menopausal women and women who are
	menopausal for < 2 years. In case the sampling
	date for serum pregnancy testing exceeds 7 days
	before treatment start, a urine test is required for
	confirmation of the absence of pregnancy.
Lung function	Body plethysmography / blood gas analysis,
	diffusion capacity
Hematology	Hemoglobin, erythrocytes, platelets, leukocytes,
	absolute neutrophils (ANC), basophils, eosinophils,
	lymphocytes, monocytes
Clinical chemistry	Sodium, potassium, calcium, magnesium, albumin
	phosphate, AST, ALT, PTT/INR, LDH, total
	bilirubin, creatinine, creatinine clearance (see
	section 18.4 Appendix 4), TSH
tumor marker	CEA, Cyfra 21-1

5.2.2 Treatment Phase

For V1 no particular assessments are required. However, the following assessments need to be repeated if the Screening assessment is older than 7 days measured from first dose of IMP: Hematology, pregnancy test, clinical chemistry, coagulation, vital signs. ConMed and AE documentation may need to be updated if required.

During treatment phase the following assessments and procedures will be performed for V2 unless a different time point is mentioned specifically:

Cardiac evaluation	12-lead ECG, transthoracic echocardiogram (TTE)
	if clinically indicated
Physical examinations and	Physical examination
vital signs	Body weight, BSA
	Vital signs measurements will include body
	temperature, pulse and blood pressure
ECOG performance status	Day 1 of each immunotherapy cycle, see
	Appendix 1 – ECOG Performance Status
Pregnancy test	During treatment phase the pregnancy test should
	be repeated if the investigator considers it
	necessary. A serum or urine pregnancy test will be
	performed in pre-menopausal women and women
	who are menopausal for < 2 years.
Hematology	Hemoglobin, erythrocytes, platelets, leukocytes,
	absolute neutrophils (ANC), basophils, eosinophils,
	lymphocytes, monocytes
Clinical chemistry +	Sodium, potassium, calcium, magnesium,
coagulation	phosphate, AST, ALT, PTT/INR, LDH, total bilirubin,
	creatinine, creatinine clearance (see section 18.4
	Appendix 4)TSH. If rising TSH is detected, a full
	assessment of fT3 and fT4 shall be performed and
	signs of hormone depletion shall be monitored
	clinically.
Concomitant medication,	Assessed on an ongoing basis

Adverse events

5.2.3 Pre-surgical visit

Tumor measurement	See section 5.1.1
according to RECIST 1.1	
(CT or MRI)	
Tumor assessments	Whole body PET-CT
CT or MRI	
Cardiac evaluation	12-lead ECG
Physical examination and	 Physical examination
vital signs	○ weight
	\circ Vital signs measurements will include body
	temperature, pulse and blood pressure
ECOG performance status	See Appendix 1 – ECOG Performance Status
Serum pregnancy test	A serum pregnancy test will be performed in pre-
	menopausal women and women who are
	menopausal for < 2 years if clinically indicated.
Lung function	Body plethymography / blood gas values
Hematology	Hemoglobin, erythrocytes, platelets, leukocytes,
	absolute neutrophils (ANC), basophils, eosinophils,
	lymphocytes, monocytes
Clinical chemistry +	Sodium, potassium, calcium, magnesium,
coagulation	phosphate, AST, ALT, PTT/INR, LDH, total bilirubin,
	albumin, creatinine, creatinine clearance (see
	section 18.4 Appendix 4), TSH
Concomitant medication,	Assessed on an ongoing basis
Adverse events	

5.2.4 Discharge visit

Hematology	Hemoglobin, erythrocytes, platelets, leukocytes,
	absolute neutrophils (ANC), basophils, eosinophils,
	lymphocytes, monocytes
Clinical chemistry +	Sodium, potassium, calcium, magnesium,
coagulation	phosphate, AST, ALT, PTT/INR, LDH, total
	bilirubin, creatinine, creatinine clearance (see
	section 18.4 Appendix 4), TSH
Concomitant medication,	Assessed on an ongoing basis + peri-operative
Adverse events	complications
Post-op. tumor tissue	Regression grading accord. to Junker criteria (see
analysis	section 18.3 Appendix 3)

5.2.5 End of Treatment Visit

Cardiac evaluation	12-lead ECG	
Physical examination and	 Physical examination 	
vital signs	o weight	
	 Vital signs measurements will include body 	
	temperature, pulse and blood pressure	
ECOG performance status	See Appendix 1 – ECOG Performance Status	
Lung function	Body plethymography / blood gas values	
Hematology	Hemoglobin, erythrocytes, platelets, leukocytes,	
	absolute neutrophils (ANC), basophils, eosinophils,	
	lymphocytes, monocytes	
Clinical chemistry +	Sodium, potassium, calcium, magnesium,	
coagulation	phosphate, AST, ALT, PTT/INR, LDH, total bilirubin,	
	albumin, creatinine, creatinine clearance (see	
	section 18.4 Appendix 4), TSH	
Concomitant medication,	Including peri-operative complications	
Adverse events		

5.2.6 Follow-up

AIO-Studien-gGmbH

After discontinuation of treatment, all patients will be followed-up for survival every 3 months. First visit of the follow-up period will take place 3 months after EOT visit. Follow-up of the individual patient will continue until death or until study is terminated. The following information will be collected during the follow-up:

- Survival data
- Subsequent anti-cancer therapy
- Study drug related adverse events continuing from treatment phase will be followed-up until the event has resolved or stabilized

5.2.7 End of Study

The final statistical analysis will be performed when the last patient has completed at least 24 months of follow-up or death occurred, whichever comes first.

5.2.8 Planned Treatment of the Patient after End of Treatment Phase

After completion of study at the End-of-Treatment-Visit, patients will generally be treated at the discretion of the investigator according to medical routine.

5.3 Removal of Patients from Treatment

Patients will be free to discontinue treatment or withdraw from the study at any time, for any reason, or they may be withdrawn/removed if necessary, to protect their health (see reasons for withdrawal below). It is understood by all concerned that an excessive rate of withdrawals can render the study uninterpretable; therefore, unnecessary withdrawal of patients should be avoided. Patients that will be withdrawn from the study will not be replaced.

Patients will be removed from further treatment for the following reasons:

- Disease progression
- Continued unacceptable toxicities despite optimal treatment or dose reduction
- During the treatment a delay of study treatment of more than 6 weeks
- Delay from screening to start of study treatment of more than 31 days
- Intercurrent illness, at the investigator's discretion
- Withdrawal of consent

- Non-compliance / Lost to follow-up
- Pregnancy
- Termination of the study by the sponsor

If there is a medical reason for withdrawal of treatment, the patient will remain under the supervision of the investigator until the AEs have been resolved or declined to baseline values.

If a patient has failed to attend scheduled assessments in the study, the investigator must determine the reasons and circumstances as completely and accurately as possible.

In case of premature discontinuation of the study treatment, the investigations scheduled for the EOT and the Follow-up visits should be performed, if possible. In any case, the eCRF section entitled "End of Treatment" must be completed.

Should a patient decide to withdraw, all efforts will be made to complete and report the observations as thoroughly as possible. The investigator should contact the patient to determine as completely as possible the reason for the withdrawal. A complete final evaluation at the time of the patient's withdrawal should be made with an explanation of why the patient is withdrawing from the study. If the reason for removal of a patient from the study is an adverse event or an abnormal laboratory test result, the principal specific event or test will be recorded on the eCRF.

If a patient withdraws consent for further study treatment, the patient should still be followed for progression and survival. If a patient withdraws consent for further participation in the study, follow-up assessments will be discontinued.

5.4 Study discontinuation

The whole study will be stopped at the discretion of the sponsor (with or without IDMC recommendation) in the event of any of the following:

- Medical or ethical reasons affecting the continued performance of the study
- Difficulties in the recruitment of patients

- Occurrence of AEs unknown to date in respect of their nature, severity, and duration or the unexpected incidence of known AE with a negative impact on the risk/benefit assessment
- Negative benefit/risk assessment due to new information
- Further external scientific evidence that this regimen might result in a suboptimal risk-benefit-assessment for the whole group of patients or for a distinct subgroup
- medically unacceptable risks for the treatment of the patients
- At the interim analysis, if the rate of unresectability is equal or greater 20%; i.e. if 3/15 or more study subjects did not undergo surgery as planned according to the protocol (unresectable or excessive delay of surgery). [early stopping rule]

6 Investigational Product

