Neoadjuvant immunotherapy benefits: may convey а number of Immunotherapeutics/checkpoint-inhibitors have demonstrated significant improvements in tumor size reduction, which potentially results in increased operability. Reduced toxicities and the simplicity of the treatment protocol may similarly increase operability due to increased compliance and efficacy. A neoadjuvant approach may be more advantageous compared to an adjuvant treatment since it is speculated that an intact blood supply of the tumor is a prerequisite for an efficient immune-surveillance and enhances immune-cell-tumor cell interaction and ultimately tumor cell killing. Furthermore, immunotherapeutics such as pembrolizumab are hypothesized to exert anti-tumor activity through the eradication or prevention of micrometastasis, resulting in extended disease free intervals and increased overall survival. In summary, we consider the risk-benefit ratio to favor the conduct of this trial. As additional safety measure, an independent data monitoring committee will review patient safety at a planned interim analysis after 15 study subjects have been treated with preoperative intent and will give recommendations with regard to trial continuation or early termination.

2 Objectives of the Study

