8.2 Sample Size Calculation

A phase II approach will be used to generate preliminary hypothesis generating data. No formal sample size estimation has been performed. The scope is to gather information on feasibility, safety and efficacy.

Target sample size is N=30

The rationale for the sample size of this trial is based on ethical, clinical as well as scientific considerations. The neo-adjuvant treatment approach with an immune check-point inhibitor is highly experimental with only limited data on safety and feasibility available. Therefore, only a small number of patients should be subjected to this experimental treatment. Nevertheless, the sample size should allow the generation of statistically meaningful evidence for feasibility and safety to permit the decision to further develop this treatment approach.

With a sample size of N=30 and assuming that the number of events follows a binomial distribution B(30,p), events with an incidence rate p > 9.5% will be observed at least once with a 95% probability. This observation limit will exclude individual pembrolizumab related SAEs but covers most of the historical reference events/rates of the primary endpoints in this trial as well as the early stopping rule.

The degree of the potential evidence provided by a sample size of N=30 is summarized in Table 3.

Table 3 Reported reference data and exact CI under a sample size of N=30 [Clopper Pearson
method] [13-15]

Adverse event / endpoint	Reported Frequency	95% CI for sample size of N=30
AE rate in Pembrolizumab monotherapy	97.4%	83.9 - 100.0
trials		
Drug related AE rate in Pembrolizumab	73.7%	54.5 - 88.0
monotherapy trials *		
SAE rate in Pembrolizumab monotherapy	37.2%	20.4 - 56.7
trials *		
Drug related SAE rate in Pembrolizumab	10 %	2.1 – 26.5
monotherapy trials *		
Cumulative rate of the 5 most frequent	9.4%	1.8 – 25.7
SAEs in Pembrolizumab monotherapy		
trials and potential impact on neo-adjuvant		
treatment approach and/or surgery		
[pneumonia (3.0%), pleural effusion		
(1.7%), pneumonitis (1.6%), dyspnea		
(1.6%) and pulmonary embolism (1.5%)] *		
number of patients treated in compliance	80 %	61.4 – 92.3
with protocol / Feasibility of resection and		
early stopping rule [#]		
Radiologic response (CR or PR) per	10 %	2.1 – 26.5
RECIST 1.1 §		
Pathologic response (grade IIb or higher as	43 %	25.2 - 62.3
per Junker criteria) [§]		
* See also section 1.2.4 and IB of pembrolizur	nab	1

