8.4.4 Safety evaluation

Adverse events:

All information recorded such as onset date, stop date, duration, maximum intensity, seriousness, relationship to study drug and outcome will be listed.

Summary tables will be presented. These tables provide the number and percentage of patients with adverse events. Associated adverse event tables present the total number of patients reporting at least one specific event and the maximum toxicity grade. Thus, patients reporting more than one episode of the same event are counted only once by the worst grade per patient.

Tabulations consist of the number and percentages of patients involved per CTC category and CTC term, the highest relation to study drug, and the maximum severity. Special tables will be displayed for CTC grade III / IV adverse events and for adverse events resulting in discontinuation of the trial. Additionally, analysis will be restricted to adverse events judged to be at least possibly related to study drug.

Laboratory parameters:

Abnormal laboratory parameters will be tabulated according to incidence and severity according to NCI CTCAE V4.03 and analyzed descriptively.

9 Independent Data Monitoring Committee

An Independent Data Monitoring Committee (IDMC) has been convened to assess the safety data, and provide recommendations to the Sponsor and Coordinating Investigator upon the stop or continuation of the study. The members of the IDMC serve in their individual capacity and provide their expertise and recommendations. The IDMC will review cumulative study data to evaluate subject safety, conduct an interim analysis and reassess the risk/benefit of the study.

The role and responsibilities of the IDMC are described in detail in a separate IDMC Charter.

10 Data Quality Assurance

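### The 3-of-15 stopping criterion is read only at the interim, although the third failure among the first 15 patients already settles it

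*Protocol*

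**What the plan says.** Protocol 5.4 lists reasons for ending the study under the opening "The whole study will be stopped at the discretion of the sponsor (with or without IDMC recommendation"). The last reason is the early stopping rule, which applies "At the interim analysis, if the rate of unresectability is equal or greater 20%; i.e. if 3/15 or more study subjects" are failures. A failure, in the same sentence, is a patient who "did not undergo surgery as planned according to the protocol (unresectable or excessive delay of surgery"). The length of an excessive delay is not given.

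Protocol 1.4 fixes the timing. The IDMC reviews safety at a "planned interim analysis after 15 study subjects have been treated with preoperative intent".

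Protocol Section 9 adds "The IDMC will review cumulative study data to evaluate subject safety, conduct an interim analysis and reassess the risk/benefit of the study" and refers to a separate charter for details. The section mentions no running count of patients who miss planned surgery, no earlier look and no pause in enrolment. The SAP mentions the rule only in its sample-size text (1.4) and does not describe the interim.

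**The concern.** The criterion is a count out of a fixed 15. Once three of those patients have failed to have surgery as planned, the result is at least 3/15 whatever happens to the others. Waiting for the remaining patients adds nothing to the answer the rule gives, but it exposes them to the regimen. They have resectable disease. Protocol 1.4 names delay that makes a tumor unresectable as the general risk of the strategy, and Protocol 8.2 wants few patients exposed.

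The interim is also described by patients treated, whereas the criterion counts surgical outcomes. If treated is read as dosed, some of the 15 outcomes are not yet known when the count is due, and one pending patient can decide between 2/15 and 3/15.

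**Working it through.** **Figures stated in the plan.** 3/15 = 20.0% and 2/15 = 13.3%, so 3 is the smallest count that meets the criterion. In 8.2, 1 − 0.905^30 = 0.950 reproduces the statement about 9.5% and 95%. The Clopper-Pearson interval for 24/30 is 61.4% to 92.3%, as in Table 3. No operating characteristics are given for the stopping rule.

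**Inputs.** Limit 3 of 15 (5.4). Accrual 30 patients in about 36 months (Synopsis, 3.7), which is 0.83 per month or one every 36.5 days. Pre-surgery visit Day 43–50 and discharge Day 60–74 (Schedule of Study Assessments). Section 3.2 puts End of Treatment 6 weeks after surgery and about 4 weeks after discharge, so surgery falls about 2 weeks before discharge, near Day 46–60. The true failure rate p is an assumption, because the documents give no expected rate; 20% is the boundary of their own criterion. The lag from first dose to known outcome is also an assumption, 46 to 92 days.

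**Probability of meeting the criterion.** P(X ≥ 3), with X binomial(15, p). At p = 0.2: 1 − (0.0352 + 0.1319 + 0.2309) = 0.602. Reading the count as failures occur gives the same probability, because the third failure occurs by patient 15 exactly when X ≥ 3.

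**Position T of the third failure.** P(T = t) = C(t−1, 2) p³ (1−p)^(t−3) for t = 3 to 15. Conditional on T ≤ 15, the mean of 15 − T is the number of the first 15 who come after it. Multiplying by P(met) gives the saving averaged over all trials; at 20%, 0.602 × 4.99 = 3.0.

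**Allowing for the lag.** Some patients are already on treatment when the third failure becomes known. With evenly spaced entry, one further patient has been dosed at a lag of 46–60 days and two at 74–92 days. At p = 0.2:
- One already dosed: 4.99 − P(T ≤ 14 | met) = 4.99 − 0.552/0.602 = 4.07.
- Two already dosed: 4.07 − P(T ≤ 13 | met) = 4.07 − 0.498/0.602 = 3.24.

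The last column below gives simulated averages over the lag.

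| True failure rate | P(met), either timing | After third failure, by position, if met | Same, averaged over all trials | First dosed after it is known, if met |
|---|---|---|---|---|
| 10% | 18.4% | 3.9 | 0.7 | 2.3–2.7 |
| 20% | 60.2% | 5.0 | 3.0 | 3.2–3.7 |
| 30% | 87.3% | 6.4 | 5.6 | 4.3–5.0 |
| 40% | 97.3% | 7.8 | 7.6 | 5.6–6.4 |

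Single fixed lags, with regular or random entry, widen the 20% entry to about 3.0–4.1.

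**Patients pending at a dosing trigger.** If the trigger is the 15th first dose, 46/36.5 = 1.3 to 60/36.5 = 1.6 earlier patients still await surgery, besides the 15th. If it is the second dose, (46−21)/36.5 = 0.7 to (60−21)/36.5 = 1.1.

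**Effect on the reported failure rate.** Among trials that meet the criterion at p = 0.2, the mean of 3/T is 34%. With all 15 observed, the mean is (3 − 0.1319 − 2 × 0.2309)/0.602/15 = 27%. Both exceed 20%, and earlier stopping exceeds it by more.

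**The case against.** A single look at a fixed number of patients is a conventional and coherent design. A reader might infer that the third failure fixes the fate of the trial, and that everyone dosed afterwards is treated in breach of a stop. The documents do not support this: 5.4 leaves stopping to the sponsor, and several of its other reasons (medical or ethical grounds, a negative benefit/risk assessment, unacceptable risk) are not tied to the interim. In an open-label, single-centre trial, missed operations are visible as they occur. The IDMC charter might also contain a running count.

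A reader might also take the counts by position, 5.0 or more at 20% and above, as the patients who would be spared. They hold only when the criterion is met and when the same reporting lag applies under both timings. If the current interim fires at dosing, the lag-adjusted figures apply. At 10% the criterion is met in only 18% of trials.

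Nor do the documents establish that the interim is triggered by a first dose. The phrase in 1.4 can be read as patients who have completed the preoperative course, and the wording of 5.4 presupposes known surgical outcomes.

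These points reduce the size of the concern and its certainty, but they do not remove it. Permission to act early is not a trigger, and using the sponsor's own limit when it is reached gives up no information that the rule needs.

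**Conclusion.** The concern holds in a limited form. It is a cheap improvement to the timing of an existing criterion, not an error in the limit. As written, the criterion is assessed only at the interim, although the third patient among the first 15 without surgery as planned already determines it. Earlier assessment leaves the chance of meeting it unchanged. At a true failure rate of 20%, and if the criterion is met, about 3.2–3.7 of the first 15 would receive a first dose after the third failure is known. Averaged over all trials, the saving by position is 3.0 patients.

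These figures assume independent outcomes with a constant failure rate, planned accrual and a 46–92 day lag. They say nothing about what the unseen charter provides. The trigger date cannot be fixed for delayed patients until excessive delay is defined.

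**What to change.** In Protocol 5.4 and the IDMC charter:

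1. Keep the limit of 3. State that the sponsor and IDMC are notified, and the existing criterion assessed, as soon as a third patient among the first 15 is known not to have had surgery as planned. The stop remains at the sponsor's discretion.
2. State that the planned interim count uses 15 patients with known surgical outcome, and align the wording in 1.4.
3. Define when a delay of surgery counts as excessive. The value is for the sponsor to set; without it the trigger date for a delayed patient cannot be determined.

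The cost is a short amendment and possibly one ad hoc IDMC contact. A stopped trial would describe fewer patients, and its failure rate would be biased further upward (about 34% against 27% at a true 20%), so the report should state the stopping point beside the estimate. If the charter already has a running count, a reference to it in 5.4 is enough for the first item.
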